### 5.4. Immune studies

It is known that RCC is a typical immunogenic tumour with immune mechanisms known to play an important role in its natural history. Recent studies have also shown that TKI treatment can influence the immune system and, importantly, changes in the immune response may affect response and survival. The immune studies aim to identify immune- and cytokine-based signatures in PBMCs, plasma and urine which predict response to

axitinib treatment in RCC patients using CyTOF and luminex-based cytokine assays. These studies will also provide important information about the effect of axitinib on the immune system in RCC, and vice versa, including providing comprehensive analysis of how peripheral immune cell populations and cytokines vary during treatment with axitinib, and whether they correlate with other markers of response and resistance in RCC patients. Importantly, it will also provide essential immunological information to inform biologically driven, rational, scheduling of future studies examining combinations of axitinib and immunotherapy.

**Appendix 7– The Principles of ICH Good Clinical Practice**

1. Clinical trials should be conducted in accordance with the ethical principles that have their origin in the Declaration of Helsinki, and that are consistent with GCP and the applicable regulatory requirement(s).
2. Before a trial is initiated, foreseeable risks and inconveniences should be weighed against the anticipated benefit for the individual trial subject and society. A trial should be initiated and continued only if the anticipated benefits justify the risks.
3. The rights, safety, and well-being of the trial subjects are the most important considerations and should prevail over interests of science and society.
4. The available nonclinical and clinical information on an investigational product should be adequate to support the proposed clinical trial.
5. Clinical trials should be scientifically sound, and described in a clear, detailed protocol.
6. A trial should be conducted in compliance with the protocol that has received prior institutional review board (IRB)/independent ethics committee (IEC) approval/favourable opinion.
7. The medical care given to, and medical decisions made on behalf of, subjects should always be the responsibility of a qualified physician or, when appropriate, of a qualified dentist.
8. Each individual involved in conducting a trial should be qualified by education, training, and experience to perform his or her respective task(s).
9. Freely given informed consent should be obtained from every subject prior to clinical trial participation.
10. All clinical trial information should be recorded, handled, and stored in a way that allows its accurate reporting, interpretation and verification.
11. The confidentiality of records that could identify subjects should be protected, respecting the privacy and confidentiality rules in accordance with the applicable regulatory requirement(s).
12. Investigational products should be manufactured, handled, and stored in accordance with applicable good manufacturing practice (GMP). They should be used in accordance with the approved protocol.
13. Systems with procedures that assure the quality of every aspect of the trial should be implemented.

1.1 Primary endpoint

The primary end-point for this study is the percentage of evaluable patients with an improvement in disease as a result of taking the study drug. The definition of an improvement will vary according to the patient's Mayo Level as captured at screening:

- **For patients presenting at screening with a Mayo Classification of Level 1 or above**, an improvement in disease will be represented by a reduction in their Mayo Classification at week 9.
- **For patients presenting at screening with a Mayo Classification of Level 0**, an improvement in disease will be represented by either:
 - a change of tumor thrombus from main renal vein to branches of the renal vein (on the right);
or
 - a change of tumor thrombus from main renal vein to the renal vein lateral to the gonadal vein (on the left).

See [Section 6.1](#) for further details regarding the definition of improvement in relation to the Mayo classification and the surgical approach classification.

1.2 Secondary endpoints

Secondary endpoints are:

- % change in surgical approach
- % change in VTT length
- Response rate (RECIST)
- Evaluation of surgical morbidity assessed by Clavian-Dindo classification

2 Study design

NAXIVA is a single arm, single agent, open label, phase II feasibility study of axitinib in patients with both metastatic and non-metastatic renal cell carcinoma of clear cell histology. 20 evaluable patients will be recruited from multiple centres within the United Kingdom.

Patients who have signed informed consent and who have met all eligibility criteria will be registered into the trial.

The starting dose of axitinib will be 5mg BID, escalated to 7mg BID and then 10mg BID. A dose modification assessment will take place every 2 weeks in clinic during the 8 week pre-surgical treatment period and will be dependent on tolerability of treatment. Patients will follow an aggressive axitinib dose escalation process

within the 8 week period to a maximum of 10mg BID. Patients should stop axitinib a minimum of 36 hours and a maximum of 7 days prior to surgery in week 9.

Blood, urine and tissue samples will be taken prior to and during therapy to evaluate biomarkers of treatment response. Nephrectomy and IVC tumour thrombectomy will be planned for all patients on the trial.

Where there is diagnostic doubt at site, a central review of week 0, 3 and 9 MRI and CT scans will be conducted to determine if a patient has progressed as per RECIST 1.1 criteria. In addition, those particular patient cases will be discussed on an individual basis by the trial steering committee (TSC). In addition, a central review of scans will be carried out once all scans have been carried out to ensure that all measurements are compliant with the NAXIVA MRI SOP (v2.1).

Patients will be assessed at weeks 1, 3, 5, 7, and 9 before surgery and followed up in clinic at 6 & 12 weeks post-surgery.

3 Reporting outline

This section outlines the planned content of interim, final analyses and, if relevant, additional statistical study reports.

3.1 Interim Analysis

An interim analysis will be performed after thirteen patients have been recruited (recruitment will only be suspended for the purposes of conducting the interim analysis if no improvement in the Mayo Classification has been seen in any patients at the point where the thirteenth patient is recruited). The contents of this report are outlined in this section. Further details regarding the composition of the relevant patient populations are provided in [Section 4](#).

3.1.1 Recruitment/accrual

Data describing patient accrual, including comparison to desired targets, will be presented here ([Section 7.1](#)).

3.1.2 Early stopping rules

Stopping for reasons of futility: if zero evaluable patients have shown an improvement in disease, from screening to week 9, the trial will be stopped for futility. The rule for futility is specified in ([Section 1.1](#)) with further details set out in the efficiency analysis section ([Section 7.6.1](#)).

Stopping for reasons of patient safety: completion rates for patient safety data in the ITT population (see [Section 4.2](#) for population definition) to assess whether the early stopping rules have been violated will be prioritised for review by the DMC. Should data completion be adequate to assess the early stopping rules (i.e., complete data for thirteen patients), each rule will be assessed. If any rules are violated the trial will be stopped for reasons of patient safety. These rules are specified in [Section 5.2](#) with further details set out in the safety analysis section ([Sections 7.5.1, 7.5.2 and 7.5.3](#)).

3.1.3 Safety

Data regarding toxicities, adverse events/reactions, serious adverse events (SAEs) and suspected unexpected serious adverse reaction (SUSARs) will be provided here. These analyses will be specified further in [Section 5.1](#), with further details set out in the Toxicities ([Sections 7.5.4](#)) and Serious Adverse Events sections ([Section Error! Reference source not found.](#)).

3.1.4 Efficacy

Analyses relating to efficacy endpoints will be carried out on the evaluable population (see [Section 4.3](#) for population definition); these analyses will be further specified in [Section 6Error! Reference source not found.](#) with further details set out in the Efficacy analysis section ([Section 7.67.6.1](#)). All endpoints will also be calculated for the ITT population to ensure that the conclusions drawn are the same in the context of patient discontinuation/compliance; this will require a change in denominator where percentages are calculated ([Section 6.1Error! Reference source not found.](#)).

3.1.5 Baseline demographics

Baseline demographics will be presented for the ITT population (see [Section 7.3](#) for details).

3.2 Final Analysis

The final analysis will be performed after all data for 20 evaluable patients has been obtained. The analyses performed and the data presented is as described in [Section 3.1](#) for the interim report.

If analysis findings with regards to efficacy endpoints for the evaluable population and the ITT population conflict (see [Section 3.1.4](#)), the DMC will discuss and advise with regards to the interpretation of these results.

In addition, 80% two-sided confidence intervals (to correspond to the 10% 1-sided sample size calculation) for the proportions relevant to the efficacy endpoints will be calculated using the approach in Koyama and Chen⁵ (again using both the evaluable and ITT populations as alternative contexts).

4 Populations and sample size

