### 1.5. Trial Rationale

There is no level I or II evidence of neoadjuvant studies of targeted therapies in non-metastatic RCC VTT or upfront therapies in metastatic RCC VTT. There is level III evidence of mixed populations of RCC VTT patients (including both metastatic and non-metastatic patients) treated with a heterogeneous group of drug treatments (15, 16). The results of these studies suggest that regression in VTT is limited to sunitinib therapy (seen in 3/12=25% patients; regression not seen for bevacizumab, temsirolimus or sorafenib). With sunitinib treatment none of the patients (0/12) had an increase in the VTT level (15).

A recent prospective phase II of 12 weeks neoadjuvant axitinib in ccRCC T2-T3b, has been reported by Karam and colleagues (17). All of the patients in this study were cT3a (i.e. there were no patients with VTT). It was possible to titrate all patients up to 10mg axitinib with no grade 4/5 toxicities. 100% of patient's tumours showed response (46% patients had partial response, and 54% stable disease) and the median reduction in primary tumour diameter was 28% by week 12. The median tumour diameter reduced from 10cm to 6.9cm. The vast majority of reduction in tumour size had occurred at 7 weeks of axitinib treatment.

The results of these small studies in non-metastatic RCC patients suggest that neoadjuvant TKI treatment of RCC patients is safe. However, the effect of these drugs on the extent of the VTT and the surgical approach that must be applied has not been confirmed. Authors in this field agree that a prospective trial is required to answer this important clinical question (15,16,18).

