4.1 Sample Size Calculations and recruitment schedule

The aim is to recruit 20 patients over a 24 month period. A Simon two stage minimax design to distinguish a <5% from a >25% improvement in the Mayo classification requires 20 evaluable patients (90% power, 10% 1-sided).

Thirteen patients would be recruited in the first stage. If no patients demonstrate an improvement in their Mayo classification between screening and week 9, accrual to the clinical trial would stop (see [Section 3.1.2](#)). If one or more patients demonstrate an improvement in the Mayo classification between screening and week 9, a further seven patients would be recruited (to the final total of 20 evaluable patients). In order for the clinical trial to be considered a success, at least three evaluable patients should demonstrate an improvement in disease or treatment between screening and week 9 (see [Section 7.6.1](#)).

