- The percentage of patients who have had a change in the surgical approach will be calculated with the percentage with a less invasive and the percentage with a more invasive approach shown separately. Two pieces of data are relevant here: (1) a change from “Open Surgery” to “Minimally invasive surgery”; and (2) a change from a more invasive open to a less invasive open surgical approach (see [Section 6.1](#) for a definition of surgical approach in this respect). Percentages will be calculated using both the evaluable population and the ITT population.
- The response rate, as determined by RECIST criteria v1.1 and provided by sites will be presented and the percentage of outcomes categorised as complete response, partial response and progressive disease shown; only pre-surgical timepoints (i.e., weeks 3 and 9) will be considered. To provide further quality assurance that these RECIST evaluations are correct, the RECIST response will be recalculated from source data by the study statistician and compared to the evaluations provided by sites. Should the evaluations not correspond with each other, a data query will be raised with the sites.
- Morbidity, in terms of the Clavien-Dindo classification system will be presented and percentage of patients with complications of grade I to V will be presented. Percentages will be calculated using both the evaluable population and the ITT population.

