7.7 Additional analyses

The correlation of the drug exposure with the response of the VTT will be examined by presenting the Pearson's correlation coefficient between the total dose of drug received and the percent reduction in VTT.

8 Statistical Methods for the Analysis of the Study Data

As this is a single arm feasibility study results will be presented as counts, frequencies and percentages. 80% confidence intervals will be provided for the percentage of evaluable patients with an improvement in their Mayo Classification between screening and week 9, percentage change in surgical approach and percentage change in VTT height.

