8.1 Methods for handling missing values

As part of the trial management process missing data is closely managed with the intention of minimising the amount of missing data to the lowest level possible. Particular attention will be placed upon primary and secondary end point data.

SCTRU will regularly review the data for compliance with the protocol, and for inconsistent or missing data. Should any missing data or data anomalies be found, queries will be sent to the site for resolution. Sites are expected to respond to queries within a timeous manner.

All missing data is queried with sites and where the data cannot be sources an explanation is required and quality assurance procedures are applied to validate the quality and completeness of the data before any analysis is carried out.

Once the data has been declared as ready for analysis a missing value analysis will be carried out. This will describe the pattern of missing data, identify where the missing data are located and how extensive it is, identify pairs of variables which have missing values in multiple cases and assess if data is missing randomly.

Means, standard deviations, covariates and correlations for different missing value methods (listwise, pairwise, regression and expectation-maximisation) will be produced.

Where missing data is above an acceptable level of 10% for any primary or secondary outcome data or explanatory covariates multiple imputation will be considered.

9 Reference list

1. Eisenhauer EA, *et al.* New response evaluation criteria in solid tumours: Revised RECIST guideline (version 1.1). *Eur J Cancer* **2009**;45:228-47.
2. National Cancer Institute. Cancer Therapy Evaluation Programme. Common Terminology Criteria for Adverse Events v4.0. Available at http://ctep.cancer.gov/protocolDevelopment/electronic_applications/ctc.htm
4. Vollset, S. E. 'Confidence intervals for a binomial proportion', *Statistics in Medicine*, **12**, 809–824 (1993).
5. Koyama, Tatsuki, and Heidi Chen. "Proper inference from Simon's two-stage designs." *Statistics in medicine* vol. 27,16 (2008): 3145-54. Available at <https://onlinelibrary.wiley.com/doi/10.1002/sim.3123>.

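### SAP 3.2 applies the two-stage (Koyama-Chen) 80% interval to secondary efficacy proportions, although only the primary endpoint drives the 0-of-13 stop

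*SAP*

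**What the plan says.** SAP 3.2 (Final Analysis) specifies two-sided 80% intervals "for the proportions relevant to the efficacy endpoints will be calculated using the approach in Koyama and Chen", in both the evaluable and ITT populations. The plural is not limited to the primary endpoint. The title of the cited paper in SAP 9 is "Proper inference from Simon's two-stage designs".

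The stage-1 stop is defined on the primary endpoint alone. SAP 3.1.2 states that "if zero evaluable patients have shown an improvement in disease, from screening to week 9, the trial will be stopped for futility", and SAP 4.1 gives the same rule for the first 13 patients.

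SAP 6 and 7.6.2 place surgical approach, RECIST response and Clavien-Dindo grade under efficacy. For surgical approach, SAP 6 wants the result "with the percentage with a less invasive and the percentage with a more invasive approach shown separately".

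SAP 8 says that "80% confidence intervals will be provided for the percentage of evaluable patients with an improvement in their Mayo Classification" and adds change in surgical approach and change in thrombus height. It names no interval method and mentions only evaluable patients.

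**The concern.** A two-stage interval orders outcomes on the assumption that zero events on the analysed endpoint in stage 1 ends the trial. That is true of primary improvement. For a secondary proportion the trial can continue to 20 whatever the secondary count was in the first 13. The method's sample space is then wrong, and 0/20 is not in it. An analyst following SAP 3.2 literally would have to improvise after seeing the data.

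The result most exposed is a harm-relevant one, the share of patients who need a more invasive operation. The documents give no expected rate for it. The nearest figure is in Protocol 1.5: "With sunitinib treatment none of the patients (0/12) had an increase in the VTT level". That is another drug and another outcome, but it makes 0 or 1 events in 20 credible.

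SAP 3.2 and SAP 8 also differ in scope. The first covers all efficacy proportions in two populations; the second lists three quantities in one population.

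**Working it through.** **Design reproduced.** SAP 4.1 describes "A Simon two stage minimax design to distinguish a <5% from a >25% improvement in the Mayo classification", which "requires 20 evaluable patients (90% power, 10% 1-sided"). Inputs: p0 = 0.05, p1 = 0.25, alpha at most 0.10 one-sided, power at least 0.90. An exact search returns 13 patients in stage 1, stop at 0 improvers, 20 in total and success at 3 or more. Actual alpha is 0.0736 and power 0.9030. The plan's figures hold.

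**Formulas.** X1 is the count in the first 13 and X the total in 20, with 10% in each tail. Tail inversion is my assumption.

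- Two-stage lower limit for x events: solve P(X1 ≥ 1 and X ≥ x) = 0.10.
- Two-stage upper limit: solve 1 − P(X1 ≥ 1 and X ≥ x + 1) = 0.10.
- Comparator: single-stage Clopper-Pearson 80% with n = 20.

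**One event in 20.**

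- Two-stage lower: 1 − (1 − p)^13 = 0.10, so p = 1 − 0.9^(1/13) = 0.0081.
- Single-stage lower: p = 1 − 0.9^(1/20) = 0.0053.
- Two-stage upper: (1 − p)^13 + 13p(1 − p)^19 = 0.10 at p = 0.1954 (0.0592 + 0.0408).
- Single-stage upper: (1 − p)^20 + 20p(1 − p)^19 = 0.10 at p = 0.1810 (0.0185 + 0.0815).

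The term (1 − p)^13 treats every result with no event in the first 13 as a stopped trial. For a secondary endpoint that is false.

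**Zero events in 20.** The two-stage method has no such outcome. Borrowing the 0/13 stop gives an upper limit of 1 − 0.1^(1/13) = 16.2%; the exact limit is 1 − 0.1^(1/20) = 10.9%.

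| Events of 20 | Two-stage 80% | Clopper-Pearson 80% |
|---|---|---|
| 0 | no entry (0 to 16.2% if forced) | 0 to 10.9% |
| 1 | 0.81 to 19.5% | 0.53 to 18.1% |
| 2 | 2.86 to 24.8% | 2.69 to 24.5% |
| 3 | 5.70 to 30.5% | 5.64 to 30.4% |
| 4 | 9.04 to 36.1% | 9.02 to 36.1% |

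**How often it arises**, for a secondary category independent of the primary:

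| True rate | 0 in first 13 | of which 0/20 | of which first event in last 7 | 0 or 1 in 20 |
|---|---|---|---|---|
| 5% | 51% | 36% | 15% | 74% |
| 10% | 25% | 12% | 13% | 39% |

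At a 25% rate, 0 or 1 events in 20 has probability 2%.

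**Error rates under independence.**

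- Two-sided coverage of the two-stage interval stays at or above 80.7%.
- The upper limit misses at most 10.0% of the time.
- The lower limit can miss more than 10%. As the true rate approaches 0.81% from below, any event is a miss, with probability 1 − 0.9^(20/13) = 15.0%.
- At a 5% rate the mean upper limit is 20.3% (0/20 forced) against 17.7%. Of that 2.5-point gap, 0.358 × (16.2 − 10.9) = 1.9 points come from the forced 0/20 value and about 0.6 from the other counts.
- At a 25% rate the means are 41.2% and 41.1%.

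**The case against.** The best defence is that little goes wrong. Two-sided coverage holds, the shift at 1/20 is 0.3 point below and 1.4 points above, and nothing visible changes from 3 events. That stands, and it is why the point is minor.

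The 16.2% at 0/20 is conditional: no passage tells the analyst to treat 0/20 as 0/13. The firm statement is that the SAP gives no usable method for 0/20.

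One can also read SAP 3.2 as giving the method and SAP 8 as giving the quantities, which would leave RECIST and Clavien-Dindo without intervals. Surgical approach remains even then. SAP 8 does not say outright that the more invasive share gets its own interval, but SAP 6 and 7.6.2 report the two directions as separate percentages.

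Independence is an assumption. Protocol 1.5 links thrombus extent to surgical extent, so the less invasive share should track the primary, and the closer it does so the better the two-stage interval fits. The argument is strongest for categories that do not track improvement, such as more invasive surgery or complication grades.

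Finally, the more invasive share may be related to the safety rule that closes the trial after three thrombus extensions (SAP 5.2). Neither interval accounts for that rule, and the check of the fix did not include it.

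**Conclusion.** The concern holds and is minor. As written, SAP 3.2 attaches a two-stage interval to proportions that do not drive the two-stage stop. The effect is confined to rare secondary categories: no defined interval at 0/20, limits of 0.8% to 19.5% instead of 0.5% to 18.1% at 1/20, and differences of at most 0.35 point at 2/20. The upper limit is too high and the lower limit slightly too high, so the net effect is mostly unnecessary width, with a lower-tail miss above 10% only for near-zero rates.

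The decimals rest on tail inversion, the design stage sizes of 13 and 20, and, for the probabilities and error rates, independence from the primary. The success rule, alpha, power and evaluable-population primary interval do not change. The mismatch in scope between SAP 3.2 and SAP 8 needs no calculation and stands on the text.

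**What to change.** 1. In SAP 3.2, restrict the two-stage interval to the primary improvement proportion: evaluable population with its actual stage sizes, and ITT with the actual ITT stage-1 and total sizes. State the inversion convention. Clopper-Pearson should not replace it there: just above p = 0.181 both the 0/13 stop and 1/20 would miss from below, with probability 0.819^13 + 13 × 0.181 × 0.819^19 = 0.075 + 0.053 = 12.8%.
2. For every other proportion, in either population, specify an exact Clopper-Pearson 80% interval at the actual N (13 if the trial stops at stage 1, otherwise the final number). Continuing past stage 1 selects slightly on any outcome related to the primary, so this was checked with primary rates from 5% to 35% and association from the most negative to the most positive possible. Total coverage did not fall below 80.1%.
3. List in one place which proportions get an interval and in which population, so that SAP 3.2 and SAP 8 agree. Say explicitly whether the less and more invasive shares each get one.
4. As a clarification only, name the summary (mean or median) and interval for percentage change in thrombus length, which is not a proportion and has no stated method in SAP 8.

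The cost is a few sentences in SAP 3.2 and SAP 8 and standard routines. No data collection changes.
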